5.15 Pharmacodynamic Analyses

The evaluation of PD parameter will be done following endpoints.

- [REDACTED]
- [REDACTED]

QMD Ref: Worldwide-TMP-ST-054-1.0_Effective: 12Aug2022	Governing QMD: Worldwide-SOP-ST-026
Confidentiality Statement This document is the property of Worldwide Clinical Trials Inc. and may not be duplicated, copied, altered or removed from company without prior approval from Worldwide Quality Assurance or in compliance with Worldwide Standard Operating Procedures.	

Worldwide Clinical Trials Controlled Quality Management Document			
		Sponsor:	MTR-601-NHV-101
		Protocol Number:	Motric Bio
STATISTICAL ANALYSIS PLAN			

[REDACTED]

[REDACTED]

[REDACTED]

- [REDACTED]
- [REDACTED]

[REDACTED]

[REDACTED]

[REDACTED]

[REDACTED]

[REDACTED]

[REDACTED]

[REDACTED]

[REDACTED]

5.16 Safety Analyses

The safety analyses will be presented by the treatment received for the Safety Population.

5.16.1 Adverse Events

AEs will be coded by Medical Dictionary for Regulatory Activities (MedDRA). The version of MedDRA to be used in this study will be defined in the data management plan (DMP).

Treatment emergent adverse events (TEAE) are reported according to protocol as any AE that has an onset on or after the dose of study drug or any pre-existing condition that has worsened on or after the first dose of study drug.

The following TEAE flag will be applied to distinguish AEs from TEAEs:

- Any AE that has a start date and time on or after the first dose of study drug

A treatment-related AE is defined as an AE as related to the study drug. If an AE has missing relationship it is assumed to be related to the study drug for analysis purposes.

Maximum severity will be assumed for an AE with missing severity.

QMD Ref: Worldwide-TMP-ST-054-1.0_Effective: 12Aug2022	Governing QMD: Worldwide-SOP-ST-026
Confidentiality Statement This document is the property of Worldwide Clinical Trials Inc. and may not be duplicated, copied, altered or removed from company without prior approval from Worldwide Quality Assurance or in compliance with Worldwide Standard Operating Procedures.	

Worldwide Clinical Trials Controlled Quality Management Document			
		Sponsor:	MTR-601-NHV-101
		Protocol Number:	Motric Bio
STATISTICAL ANALYSIS PLAN			

The following tables will be presented for AEs incidence and/or number of events will be reported as appropriate:

- Overall summary of TEAEs
- TEAEs by system organ class and preferred term
- Treatment related TEAE by system organ class and preferred term
- Serious TEAE by system organ class and preferred term
- TEAE by system organ class, preferred term and maximum severity by system organ class, preferred term and relationship
- TEAEs leading to early withdrawal by system organ class and preferred term
- Adverse Events of Special Interest (AESIs) by system organ class and preferred term
- Listing of Serious TEAEs (presented in the Table section of the appendices).
- Listing of Deaths (presented in the Table section of the appendices).

Adverse event incidence is counted only once per system organ class and once per preferred term. The number and percent of subjects experiencing events are reported. Outputs reported at maximum severity show the highest severity reported by a patient per system organ class and preferred term.

In counting the number of AEs reported, a continuous event (i.e., reported more than once and which did not cease), will be counted only once; non-continuous AE reported several times by the same subject will be counted as multiple events.

In the AE summary tables the system organ class will be order alphabetically and the preferred term within the system organ class will be order in decreasing frequency for the Overall column. In case of tie(s), the preferred term will be ordered alphabetically.

For SAD cohort 2 the AE will be attributed to the treatment as taken based on the event date and the dosing date.

All AEs will be listed for Safety population.

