5.4. Screen Failures

Screen failures are defined as subjects who consent to participate in the clinical study but not subsequently enrolled in the study. Any subjects who screen fails will be fully documented in the source documentation. Minimal information required in the source documentation includes a completed informed consent form (ICF), demography, reasons for screen failure, and all results of all assessments and procedures completed prior to the subject being confirmed as a screen failure and any SAE that occurs after completion of the ICF.

Subjects who do not meet the criteria for participation in this study (i.e., screen failures) may be rescreened once after discussion with the Medical Monitor for non-health-of-the-subject reasons (e.g., washout from over-the-counter medication use, positive urine screen for alcohol).

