8.4.1.1. Events Meeting the Adverse Event Definition

Events Meeting the AE Definition

- Laboratory test results outside the normal range (hematology, clinical chemistry, or urinalysis) or other safety assessments (e.g., ECG, vital signs measurements), including any that worsen in severity grade (see Section 8.4.4.3) from baseline, which are considered clinically significant in the medical and scientific judgment of the Investigator.
- Exacerbation of a chronic or intermittent pre-existing condition resulting in an increase in severity grade.
- Condition detected or diagnosed that is new in onset or increased in severity grade from the baseline condition.
- Signs, symptoms, or the clinical sequelae of a suspected intervention-intervention interaction.
- Signs, symptoms, or the clinical sequelae of a suspected overdose of either study treatment or a concomitant medication. An overdose or incorrect administration of study treatment is not itself an AE, but it may result in an AE.

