8.4.3. Time Period for Collecting AE and SAE Information

All SAEs and AEs will be recorded from first dose of study medication (see Section 8.3.1.1 regarding laboratory-associated AE assessments).

If the Investigator becomes aware of an SAE any time after the Follow-up telephone call, the Sponsor should be notified immediately (i.e., within 24 hours). Report the SAE using the method described below Section 8.4.5.

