8.4.4.3. Severity of Adverse Events

Severity of AEs will be graded as:

- **Mild:** event may be noticeable to the subject; does not influence daily activities; usually does not require intervention
- **Moderate:** event may be of sufficient severity to make the subject uncomfortable; performance of daily activities may be influenced; intervention may be needed
- **Severe:** event may cause severe discomfort; usually interferes with daily activities; subject may not be able to continue in the study; treatment or other intervention usually needed

If the severity of an AE changes more than once a day, the maximum severity for the event should be listed. If the severity changes over a number of days, these mini-events or changes should be recorded separately (i.e., having distinct onset dates).

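### SAP 5.16.1 counts worsened pre-existing conditions as treatment-emergent, but the flag that applies the definition tests only the AE start date and time

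*SAP*

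**What the plan says.** SAP 5.16.1 gives a definition and then a rule that applies it.

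- Definition, first limb: "any AE that has an onset on or after the dose of study drug".
- Definition, second limb: "any pre-existing condition that has worsened on or after the first dose of study drug".
- Rule: "The following TEAE flag will be applied to distinguish AEs from TEAEs", followed by a single bullet, "Any AE that has a start date and time on or after the first dose of study drug".

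The rule has no worsening criterion.

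Three protocol provisions bear on it. Section 8.4.1.1 counts as an AE "Exacerbation of a chronic or intermittent pre-existing condition resulting in an increase in severity grade". Section 8.4.3 sets the collection window: "All SAEs and AEs will be recorded from first dose of study medication". Section 8.4.4.3 says that when the severity of an AE changes over several days, "these mini-events or changes should be recorded separately (i.e., having distinct onset dates".

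SAP 5.16.1 also assigns AEs in SAD cohort 2 to the fasted or fed dose by comparing the event date with the dosing dates. SAP 5.2.5.1 treats an AE as treatment-emergent when a missing start date or time leaves the matter unclear.

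**The concern.** The definition and the rule in the same subsection do not select the same events. A programmer who follows the rule will leave unflagged any AE that began before dosing and worsened afterwards, although the definition counts it.

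The number and incidence of TEAEs is the first component of the primary endpoint (Protocol 3, SAP 2). By their titles in SAP 10, the tables by system organ class and preferred term, and those for treatment-related, serious, maximum-severity, relationship, withdrawal and special-interest events, are all restricted to treatment-emergent events. An unflagged event is absent from all of them.

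The population can contain such conditions. Exclusion criterion 6 admits disorders judged not clinically significant. Inclusion criterion 7 does the same for out-of-range laboratory results. Exclusion criterion 30 removes only IPSS scores of 6 or more. SAP 5.8 plans a table of conditions ongoing at screening.

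**Working it through.** The plan gives no count of such events, so the main check is a comparison of the definition (D) with the flag (F).

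- D = start on or after first dose, OR pre-existing and worsened on or after first dose.
- F = start on or after first dose.

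Every event in F is in D. The events in D but not in F are those that start before first dose and worsen on or after it.

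| AE record | In D? | In F? | Result |
|---|---|---|---|
| Starts on or after first dose | Yes | Yes | Tabulated |
| Starts before first dose, worsens on or after it | Yes | No | Left out of TEAE tables |
| Starts before first dose, does not worsen | No | No | Properly left out |

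The third row should be rare in dosed subjects, because Protocol 8.4.3 begins AE recording at first dose. The one pre-dose provision found, "any SAE that occurs after completion of the ICF" in Protocol 5.4, concerns screen failures, who are not in the Safety Population.

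The next question is whether another provision closes the second row.

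- Protocol 8.4.4.3 asks for new onset dates when the severity of an AE changes. A medical-history condition was not an AE before dosing, and the section does not say which date its worsening takes.
- SAP 5.2.5.1 helps only when a date or time is missing. A known pre-dose start gets no benefit from it.
- Protocol 8.4.4.1 requires start and stop dates for each AE but sets no dating convention for an exacerbation.

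Size of effect for one affected subject, assuming all planned cohorts enrol in full (SAP 4: 6 active and 2 placebo per cohort; SAP 5.3: placebo pooled within SAD and within MAD):

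- Active cohort: 1/6 = 16.7 percentage points.
- Pooled SAD placebo: 5 × 2 = 10 subjects, so 1/10 = 10 points.
- Pooled MAD placebo: 6 × 2 = 12 subjects, so 1/12 = 8.3 points.

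SAP 5.16.1 counts a subject once per system organ class and once per preferred term. Overall TEAE incidence therefore moves by these amounts only if the subject has no other TEAE; otherwise only the affected class or term rows change.

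**The case against.** The strongest reply is that the flag will work in practice. Protocol 8.4.1.1 makes the exacerbation itself the AE, and 8.4.3 records AEs from first dose. The natural record therefore starts at the worsening, and the underlying condition stays in medical history, which has its own tables. Section 8.4.4.3 points the same way, and nothing tells sites to enter the historical onset date. Detailed dating rules often sit in eCRF completion guidelines, which are not among the documents supplied.

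This stands as far as it goes: the loss depends on how sites date the record, and on that reading there is none. It does not remove the mismatch, because the dating convention is not written in either document. If every worsening were dated at worsening, the second limb of the definition would also be unnecessary. It matters only for records with a pre-dose start, and those are the records the flag leaves out.

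A reader might infer more than the documents support:

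- *That the flag's only effect is to delete worsened conditions.* A record dated at worsening is kept. A pre-dose event entered despite 8.4.3 is rightly excluded, and the time component of the flag allows this even on Day 1.
- *That an unflagged event survives only in the all-AE listing.* Listing 16.2.7.2 (serious adverse events) and the death listings, 14.3.2.3 and 14.3.2.4, are not titled as restricted to treatment-emergent events.
- *That subject protection is weakened.* The stopping rules in Protocol 4.1 and 4.1.1 and in SAP 7 refer to AEs, SAEs and measured values, not to the flag.

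**Conclusion.** The point holds as a definite inconsistency with a conditional consequence. An AE with a known pre-dose start that worsens after dosing is treatment-emergent by the SAP's definition and not by its flag. The effect is confined to TEAE reporting. It arises only if at least one worsened condition is entered with its original onset date, which neither document rules out.

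The documents do not allow the frequency to be estimated. In screened healthy volunteers aged 18–45 it is probably low. The percentage-point figures above show how much one subject weighs in small cohorts; they do not forecast bias. This is a minor correction, but it concerns the first component of the primary endpoint and is best settled before database lock. Under SAP 5, analysis changes after lock need an addendum.

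**What to change.** Make two linked changes.

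1. In SAP 5.16.1, extend the flag so that an AE is treatment-emergent if its start date and time are on or after first dose, or if it is recorded as a worsening of a pre-existing condition on or after first dose.
2. In the eCRF completion instructions, state that such a worsening is entered as a new AE record whose start is the date and time of worsening.

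The second change does most of the work. It also allows the SAD cohort 2 rule to operate, since a record dated before both doses cannot be assigned to the fasted or fed dose by event date. The first change brings the rule into line with the definition and covers records already entered another way. Protocol 8.4.4.1 lists no field that marks an AE as a worsening, so any Safety Population record with a pre-dose start should be checked against medical history before lock. That check should include the cohorts already completed (Protocol 2.3: SAD 1–4 and MAD 1–3).

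The cost is one SAP line, one eCRF completion instruction and a short review of any such records. No new data collection is needed.

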4.1.2. Study Duration

Subjects Planned:	Duration of IP for each subject by dose level cohort:		
Approximately 88	SAD: 1 day	SAD Two-Dose: 2 days	MAD: 14 days
Total study duration for each subject:			
SAD:	A (maximum) 30-day screening period, check-in to the CRU on Day -1, a single dose of study medication on Day 1 with subsequent in-house observation of at least 96 hours ^a , check-out/discharge from the CRU, and a telephone follow-up on Day 7. The total duration will be approximately 37 days.		
SAD Two-Dose:	A (maximum) 30-day screening period, check-in to CRU on Day -1, a single dose of study medication on Day 1, a 4-day washout period, a second single dose of study medication on Day 6 with subsequent in-house observation of at least 96 hours ^a , check-out/discharge from the CRU, and a telephone follow-up on Day 12. The total duration will be approximately 42 days.		
MAD:	A (maximum) 30-day screening period, check-in to the CRU on Day -1, daily dosing of study medication on Days 1–14 with subsequent in-house observation of at least 96 hours ^a after the last dose, check-out/discharge from the CRU, and a telephone follow-up on Day 20. The total duration will be approximately 50 days.		

- a. If needed (e.g., in the event of AEs), the in-house observation period may be prolonged for safety observation at the discretion of the Investigator, which will extend duration of study participation by the number of additional observation days required.

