7. DISCONTINUATION OF STUDY TREATMENT, SUBJECT WITHDRAWAL, AND SUBJECT REPLACEMENT

7.1. Discontinuation of Study Treatment

A subject must be discontinued from study treatment for any of the following:

1. Withdrawal of consent to further follow-up assessments, irrespective of the reason. Note: a subject may withdraw consent to receive further study drug but should be requested to allow follow up for safety and collection of other follow up data.
2. Unable to remain under medical supervision.
3. Investigator decision (may include the need for other therapy not otherwise permitted in the study; any clinically relevant sign, symptom, or intercurrent illness that, in the opinion of the Investigator [or designee], warrants subject withdrawal).
4. Noncompliance with the study restrictions that might affect subject safety or study assessments/objectives, as considered applicable by the Investigator (or designee).
5. Change in compliance with any inclusion/exclusion criterion that is clinically relevant and affects subject safety as determined by the Investigator (or designee).
6. Has an SAE.
7. Meets any of the hepatotoxicity criteria detailed in [Table 5](#).
8. Death.

The Investigator must contact the Sponsor immediately to discuss whether to suspend dosing if an AE or laboratory abnormalities indicate that continued dosing of subsequent subjects would not be tolerated or would jeopardize the subjects' safety.

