5.2.6 Exposure to Study Drug

Exposure to study drug will be calculated (in days) as follows from the date of last dosing minus the first day of dosing + 1.

QMD Ref: Worldwide-TMP-ST-054-1.0_Effective: 12Aug2022	Governing QMD: Worldwide-SOP-ST-026
Confidentiality Statement This document is the property of Worldwide Clinical Trials Inc. and may not be duplicated, copied, altered or removed from company without prior approval from Worldwide Quality Assurance or in compliance with Worldwide Standard Operating Procedures.	

Worldwide Clinical Trials Controlled Quality Management Document			
		Sponsor:	MTR-601-NHV-101
		Protocol Number:	Motric Bio
STATISTICAL ANALYSIS PLAN			

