5.4 Subject Disposition

Subject disposition will be summarized as follows:

- The number of subjects who failed screening and the reasons for failure will be tabulated for all screened subjects.
- The number of subjects, who entered the study, were randomized and who are in each population, those who completed will be summarized by treatment cohort and overall, for all enrolled population.

QMD Ref: Worldwide-TMP-ST-054-1.0_Effective: 12Aug2022	Governing QMD: Worldwide-SOP-ST-026
Confidentiality Statement This document is the property of Worldwide Clinical Trials Inc. and may not be duplicated, copied, altered or removed from company without prior approval from Worldwide Quality Assurance or in compliance with Worldwide Standard Operating Procedures.	

Worldwide Clinical Trials Controlled Quality Management Document			
		Sponsor:	MTR-601-NHV-101
		Protocol Number:	Motric Bio
STATISTICAL ANALYSIS PLAN			

- The number of early withdrawals and the reasons for withdrawals will be tabulated by treatment cohort and overall, for the safety population.

Subjects excluded from the analysis populations and the reason for their exclusion will be summarized and listed.

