5.11 Exposure to Study Drug

All dosing will be listed for Safety Population.

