14.3.1.15	Treatment-Emergent Adverse Events Leading to Early Termination/Withdrawal by Primary System Organ Class and Preferred Term - SAD Safety Population	IP	
14.3.1.16	Treatment-Emergent Adverse Events Leading to Early Termination/Withdrawal by Primary System Organ Class and Preferred Term - MAD Safety Population	IP	
14.3.1.17	Treatment-Emergent Adverse Events of Special Interest by Primary System Organ Class and Preferred Term - SAD Safety Population	IP	
14.3.1.18	Treatment-Emergent Adverse Events of Special Interest by Primary System Organ Class and Preferred Term - MAD Safety Population	IP	
14.3.2	Listings of Deaths, Other Serious and Significant Adverse Events		
14.3.2.1	Listing of Serious TEAEs - SAD Safety Population	IP	
14.3.2.2	Listing of Serious TEAEs - MAD Safety Population	IP	
14.3.2.3	Listing of Deaths - SAD Safety Population	IP	
14.3.2.4	Listing of Deaths - MAD Safety Population	IP	
14.3.2.5	Listing of TEAEs Leading to Study Withdrawal - SAD Safety Population	IP	

QMD Ref: Worldwide-TMP-ST-054-1.0_Effective: 12Aug2022	Governing QMD: Worldwide-SOP-ST-026
--	-------------------------------------

Confidentiality Statement

This document is the property of Worldwide Clinical Trials Inc. and may not be duplicated, copied, altered or removed from company without prior approval from Worldwide Quality Assurance or in compliance with Worldwide Standard Operating Procedures.

Worldwide Clinical Trials Controlled Quality Management Document			
		Sponsor:	MTR-601-NHV-101
		Protocol Number:	Motric Bio
STATISTICAL ANALYSIS PLAN			

Table Number	Table Title	Validation Method	Shell Number (if repeat)
14.3.2.6	Listing of TEAEs Leading to Study Withdrawal - MAD Safety Population	IP	
14.3.4	Abnormal Laboratory Values		
14.3.4.1	Laboratory, Abnormal Values - SAD Safety Population	IP	
14.3.4.2	Laboratory, Abnormal Values - MAD Safety Population	IP	
14.3.6	Vital Signs and Physical Examination		
14.3.6.1	Vital Signs Data, Descriptive Statistics - SAD Safety Population	IP	
14.3.6.2	Vital Signs Data, Descriptive Statistics - MAD Safety Population	IP	
14.3.6.3	Physical Examination Data, Shift Summary - SAD Safety Population	IP	
14.3.6.4	Physical Examination Data, Shift Summary - MAD Safety Population	IP	
14.3.6.5	Neurological Examination Data, Shift Summary - SAD Safety Population	IP	
14.3.6.6	Neurological Examination Data, Shift Summary - MAD Safety Population	IP	
14.3.7	Other Safety		
14.3.7.1	Hematology Data, Descriptive Statistics - SAD Safety Population	IP	

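### The SAP tabulates adverse events leading to study withdrawal but not to stopping study drug, and its exposure rule gives 6 days for the Two-Dose cohort where the protocol states 2

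*SAP*

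**What the plan says.** **Two events in the protocol.** Section 7.1 lists when study treatment must stop. The list includes an SAE and the hepatotoxicity criteria of Table 5. Section 7.2 lists when a subject leaves the study altogether, which it describes as having no further follow-up; neither of those two reasons is in that list. A note under the consent item of 7.1 foresees a subject who is off drug but still observed: "a subject may withdraw consent to receive further study drug but should be requested to allow follow up for safety".

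**One event in the SAP.** Section 5.16.1 plans "TEAEs leading to early withdrawal by system organ class and preferred term". In the list of outputs (section 10), Tables 14.3.1.15 and 14.3.1.16 carry this forward; the MAD title is "Treatment-Emergent Adverse Events Leading to Early Termination/Withdrawal by Primary System Organ Class and Preferred Term - MAD Safety Population". Listings 14.3.2.5 and 14.3.2.6 are worded at study level, for example "Listing of TEAEs Leading to Study Withdrawal - SAD Safety Population". For disposition, section 5.4 counts completers and adds: "The number of early withdrawals and the reasons for withdrawals will be tabulated by treatment cohort and overall, for the safety population". The SAP defines neither term, and no output title or disposition item names discontinuation of study drug. Treatment compliance (5.12) is marked not applicable.

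**Exposure.** SAP 5.2.6 calculates days of exposure "from the date of last dosing minus the first day of dosing + 1". SAP 5.11 says: "All dosing will be listed for Safety Population". Section 10 contains a dosing listing (16.2.5.1) but no exposure summary table. Protocol 4.1.2 gives the duration of IP as 1 day for SAD and 14 days for MAD, with "SAD Two-Dose: 2 days".

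**The concern.** The primary objective is the safety and tolerability of single and multiple doses. Where dosing runs for 14 days, the number of subjects who could not stay on drug because of an adverse event is one of the plainest tolerability results. If the tables count only departures from the study, a subject who stops drug and is then kept for follow-up can be missed. Good retention after a drug stop would then make tolerability look better in the tables.

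Because the terms are undefined, two subjects with the same course could also be coded differently, one as withdrawn and one as a completer. With 6 active subjects per cohort, one such coding choice changes what a cohort column shows.

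The exposure rule raises a smaller question: whether the derived number of days means what the protocol means by duration of IP.

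**Working it through.** **Step 1. Where an adverse-event-led drug stop would be counted.**

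| Situation | Protocol 7.1 (stop drug) | Protocol 7.2 (leave study) | SAP discontinuation output |
|---|---|---|---|
| SAE | listed | not listed | only if coded as early withdrawal |
| Table 5 hepatotoxicity criteria | listed | not listed | only if coded as early withdrawal |
| Other Table 5 individual rules | not named; can enter through investigator decision | not named; can enter through investigator decision | depends on coding |
| Consent withdrawn for drug only | foreseen in the note | same note repeated | depends on coding |

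The first two rows are the clearest. The protocol requires drug to stop and does not, in 7.2, require the subject to leave. A MAD subject who stops drug this way and completes the Day 20 call fits no SAP output title unless the site also records a withdrawal.

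**Step 2. Which cohorts are affected.** Stopping drug early is possible only where a dose remains: the six MAD cohorts (14 daily doses) and SAD Level 2 (Days 1 and 6). The other four SAD cohorts receive one dose, so the question does not arise there.

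**Step 3. Size per subject.** Each cohort has 6 active subjects. One subject is 1/6 = 16.7%; two would be 2/6 = 33.3%. Across the MAD part, one subject is 1/(6 × 6) = 1/36 = 2.8%.

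**Step 4. Exposure rule against the protocol's own durations.** Formula: last dose day − first dose day + 1.

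| Part | Dose days | SAP rule | Protocol 4.1.2 | Doses given |
|---|---|---|---|---|
| SAD | 1 | 1 − 1 + 1 = 1 | 1 | 1 |
| SAD Two-Dose | 1 and 6 | 6 − 1 + 1 = 6 | 2 | 2 |
| MAD | 1 to 14 | 14 − 1 + 1 = 14 | 14 | 14 |

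The rule reproduces two of the three protocol figures and gives three times the stated figure for Two-Dose. Counting doses reproduces all three.

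**Step 5. The rule under missed MAD doses.**

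| Days missed | SAP rule | Doses given |
|---|---|---|
| 8 | 14 | 13 |
| 8 and 9 | 14 | 12 |
| 8 to 10 | 14 | 11 |
| 13 and 14 | 12 | 12 |
| 8 to 14 (permanent stop) | 7 | 7 |

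Interior gaps are not registered. In the extreme, a subject dosed only on Days 1 and 14 would still have an exposure of 14 days, with 12 doses missed. Stops that run to the end of dosing are registered exactly. Interruption is not hypothetical in the plan: Protocol 8.3.1.1 names study drug interruption as a possible consequence of a laboratory abnormality.

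**The case against.** The case on the other side is substantial.

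- **The protocol itself blurs the terms.** The lead-in to Table 5 says that participation in the study may be discontinued when a rule is met, and SAP section 7 repeats this. Protocol 7.2 ends by saying that withdrawn subjects are followed until their adverse events resolve or stabilise, so continued observation does not prove that a subject was not withdrawn. Protocol 7.3 also speaks of subjects withdrawn because of adverse events. Investigator decision and noncompliance appear in both lists. Some subjects taken off drug may therefore be coded as withdrawn and be counted. This stands. It removes any certainty of under-reporting, but it also shows why a definition is needed.
- **The follow-up note is narrow.** It sits under withdrawal of consent, not under SAE or hepatotoxicity, and it recurs in 7.2. This stands. The separation rests on the two lists of reasons, not on the note.
- **The data are not lost.** Every adverse event is listed and enters the general TEAE tables, and every dose is listed. With 6 active subjects per cohort, a reader can link the two by hand. This stands. What no titled output supplies is the link itself.
- **The table shells are separate.** Rows in the overall adverse event summary or the disposition table might cover drug discontinuation. That cannot be checked from these documents.
- **Exposure.** The rule shows a permanent early stop, feeds no planned summary, and measures a calendar span rather than dosing days. Dosing is supervised in the clinical unit, so interior gaps should be few. All of this stands. The mismatch for Two-Dose remains.

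A reader might infer that a cohort with drug stops for toxicity will print as 0%, that nothing else in the report would show it, or that the exposure rule conceals early stopping. The documents support none of these: coding may capture the stop, the listings show the events and doses, and the span shortens when dosing ends early.

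**Conclusion.** The point holds in limited form and should be corrected. As written, the plan lets the same adverse-event-led drug stop be counted or missed depending on how undefined terms are applied. Each subject affected is 16.7% of a cohort's active arm. How many there will be is unknown, and the documents give no expected rate.

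The conclusion assumes that the table shells do not already carry a row for drug discontinuation and that at least some subjects taken off drug remain in the study without being recorded as withdrawn.

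On exposure, the definite finding is 6 days against the protocol's 2 for the Two-Dose cohort, plus insensitivity to interior missed doses in MAD. The consequence is small, because no planned summary uses the derived value.

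**What to change.** 1. Define discontinuation of study drug, study withdrawal and completion separately in SAP 5.4 and 5.16.1. Reconcile those definitions with Protocol 7.1 and 7.2 and with the participation wording that introduces Table 5.
2. Add a table and a listing of TEAEs leading to discontinuation of study drug for the MAD cohorts and for the SAD Two-Dose cohort. The single-dose SAD cohorts do not need them.
3. In disposition, add a row for completed study treatment beside completed study, with reasons for each kind of early stop.
4. Confirm that the eCRF records the action taken with study drug for each adverse event. Protocol 8.4.4.1 does not name it among the recorded fields. If it is absent, the link would have to be recovered from source for cohorts already dosed; Protocol 2.3 shows that SAD cohorts 1 to 4 and MAD cohorts 1 to 3 have been through an interim safety analysis.
5. Define exposure as the number of doses administered (1, 2 and 14 as planned), with the calendar span beside it if wanted.

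The cost is SAP wording, a few extra outputs and one eCRF check. Trial design and sample size are unaffected.
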